Total duration of β 2-agonist use.....	40
Number of lost parental workdays and productivity	41
Family expenses.....	42
Health care cost.....	42
Severity of asthma symptoms.....	42
Intensity of use of rescue B2-agonists.....	44

Parental functional status.....	45
Appendix 3: Coding for subgroup variables	45
Subgroup variables.....	45
Subgroups (pre-specified).....	45
Clinical Asthma Phenotype	46
Sex.....	47
Atopy.....	47
Body Mass Index (BMI) at baseline	47
Skin Color	48
Subgroups to consider (ad hoc)	48
Type 2 inflammation	48
Past Morbidity in previous 12 months	48
Prescribed GINA 4 Step-therapy at index visit.....	49

List of abbreviations

AE	Adverse event
AUC	area under the curve
CHUSJ	Centre Hospitalier Universitaire de Saint-Justine
CI	Confidence interval
CRF	Case report form
ED	Emergency department
kg	Kilogram
MD	Medical doctor
MedDRA	Medical dictionary for regulatory activities
mg	Milligram
Min	Minimum
OR	Odds ratio
SAE	Serious adverse event
SAP	Statistical analysis plan
SD	standard deviation

Introduction

Background: Preschoolers have the highest rate of acute care visits and hospitalisations of all age groups. Most exacerbations are triggered by upper respiratory tract infections (URTI), mainly in the fall/winter. New evidence suggests significant long-term sequelae of preschool asthma: irreversible lung obstruction by 6 years and chronic obstructive lung disease in adulthood. Risk factors of sequelae include frequency and severity of exacerbations, specific viral URTIs, and atopy. Prevention is the best approach to reduce morbidity. Vitamin D insufficiency is highly prevalent in Canadian preschoolers with recurrent asthma exacerbations (75%), increases further in winter, and is associated with more URTI and OCS use, indicative of moderate/severe exacerbations. A systematic 2016 review of randomised controlled trials (RCT) concluded that vitamin D supplements significantly decreased asthma exacerbations requiring rescue OCS (rate ratio: 0.63, high-quality evidence) with insufficient data to firmly conclude that findings apply to preschoolers with moderate/severe exacerbations.

Specific Objectives: To determine if vitamin D3 supplementation will reduce by 25% the number of exacerbations requiring rescue OCS per child (primary outcome), URTIs, and other markers of exacerbation frequency and severity, compared to placebo in preschoolers with moderate/severe exacerbations.

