Design: A Phase III, randomised, triple-blind, placebo-controlled, parallel-group multicentre trial of vitamin D3 supplementation. Overall, 323 (of the target of 865) children aged 1-5 years, with asthma triggered by URTI, ≥ 4 URTIs in past year (or ≥ 2 URTIs in past 12 months if pertaining to the pandemic period) and ≥ 1 OCS in the past 6 months (12 months since February 2022) were recruited in 9 or more Canadian centers over a 7-year period in this high-intensity 7-month protocol. Year-round, children were randomly assigned to one of the two following study arms: (1) Intervention—two oral boluses of 100,000 IU vitamin D3 (3.5 months apart) with 400 IU daily vitamin D3 or (2) Control—identical placebo boluses with daily placebo dose.

Research question: Can vitamin D3 supplementation decrease the number of asthma exacerbations per child requiring rescue OCS (predominantly physician-initiated) vs placebo?

Randomisation was implemented through the Applied Clinical Research Unit (ACRU), at the CHUSJ, under the direction of the study statistician, [name]. A computer-generated random list was utilized, with randomisation stratified by site to ensure balanced allocation across different locations. Children were allocated to either the vitamin D3 or placebo group in a 1:1 ratio using a permuted block randomisation method, which enhanced allocation concealment. Group allocation codes for each site were securely stored with restricted access by the Central Pharmacy (CHUSJ) and the independent biostatistician. The active vitamin D3 and placebo preparations, provided by the manufacturer Europharm, were identical in appearance and taste, ensuring blinding. The allocated treatment numbers were forwarded to site pharmacies, which prepared the bolus in coded syringes and the coded bottles containing the daily dose and dispensed the study drugs in masked kits to maintain the integrity of the randomisation process.

Analysis objectives

The primary objective of this analysis is to evaluate whether vitamin D3 supplementation leads to a 25% relative reduction in the mean number of exacerbations requiring oral corticosteroids (OCS) per child over a 7-month period compared to placebo. We hypothesized that the number of OCS per child would approximately follow a Poisson distribution.

The secondary objectives are to assess differences between the treatment groups in:

- Mean number and type of laboratory-confirmed respiratory infections during asthma exacerbations.

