- Severity of asthma symptoms during exacerbations.
- Duration of asthma symptoms during exacerbations.
- Duration of use of rescue β 2-agonists during exacerbations
- Intensity of use of rescue β 2-agonists during exacerbations.
- Parents' functional status during asthma exacerbations.
- Mean number of emergency department (ED) visits for asthma exacerbations.
- De-intensification of preventive asthma therapy at scheduled clinic visits.
- Cost-effectiveness of the intervention.
- Proportion of children with clinically significant hypercalciuria, hypercalcemia, serum 25OHD >250 nmol/L, and adverse health events.

The exploratory objectives are to examine differences between the treatment groups in:

- Gene expression changes between baseline and 3.5 months.
- White blood cells' response to infections between baseline and 3.5 months.
- Serum and nasal metabolome and blood cell composition over 7 months.
- Distribution of laboratory-confirmed respiratory infections.
- Viral load
- Lung function changes measured by respiratory resistance at 7 months.
- Markers of bone remodeling.
- Identification of responders to vitamin D in peripheral blood mononuclear cells (PBMC) or gene polymorphisms.

Finally, subgroup analyses based on baseline variables are planned to identify potential modulators of response and subgroups that may experience greater benefits from the treatment.

Data source(s) and time frame

Main REDCap database: Data was collected directly in the participant's electronic Case Report Forms (eCRF) or recorded on paper CRF before being entered into the eCRF during the study follow-up period (7 months). The set of eCRFs in the REDCap database includes the following instruments:

1. Pre Screening Form

2. Confirmation Of Eligibility And Willingness To Participate prior to randomisation (CEWP)
3. Calcium Intake
4. Vitamin D Intake
5. Pharmacy Report (verification of eligibility, documented OCS dispenses)
6. OCS documented in medical records (verification of eligibility, documented OCS administration in clinic/hospital)
7. Medical Examination (performed and completed at Clinic Visits 1,2,3)
8. Comorbidity
9. Randomization
10. Urine Collection
11. Blood Collection (clinic)
12. Blood collection (home)
13. Nasal swab (clinic)
14. Nasal swab reception (from parents) - (documented returns of nasal swabs taken by parents during cold between the clinic visits)
15. Baseline Demographics
16. Allergy and Environment
17. Visit and Phone Contact

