Potential modification of the effect of study intervention with vitamin D on primary and secondary outcomes will be assessed using the addition of interaction terms to the regression models. If there is a significant effect of the intervention, we will consider there as evidence of potential effect modification if inclusion of the interaction improves the overall model fit (using AIC/BIC criteria or R squared metrics), and if the interaction term is significant at an alpha of 0.20 or lower.

Statistical software and versions

The statistical analyses will be conducted using R 4.3.1 on Rstudio Server 2023.03.0. The following R packages are likely to be used based on the analysis requirements: base, stats, MASS, glm2, car, dplyr, tidyr, ggplot2, mice, Amelia, boot, heemod, BCEA.

Ancillary studies:

The economic evaluation will use standard trial-based economic evaluation methods. The intention is to provide the expected value of the intervention cost versus health care and family cost of exacerbations, effectiveness, and cost-effectiveness ratio with uncertainty around such values in terms of credible intervals.

References:

[name] FM, Jensen ME, Mendelson MJ, Parkin PC, Desplats E, Zhang X, Platt R. Asthma Flare-up Diary for Young Children to monitor the severity of exacerbations. *J Allergy Clin Immunol.* 2016 Mar;137(3):744-9.e6. doi: 10.1016/j.jaci.2015.07.028. Epub 2015 Sep 2. PMID: 26341275.

GINA 2024:www.ginasthma.com with ICS Doses based on Canadian Thoracic Society 2021 Guideline

Yang CL, et al. 2021 Canadian Thoracic Society Guidelines. *Can J Resp Crit Care Sleep Med.* 2021:1-41

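### The planned credible interval on the cost-effectiveness ratio cannot be interpreted if the posterior for the effect difference covers zero, and the SAP has no rule for that case

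*SAP*

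**What the plan says.** Under Analysis objectives, the SAP lists "Cost-effectiveness of the intervention" among the secondary objectives. The method is given in two sentences under Ancillary studies. The first is generic: "The economic evaluation will use standard trial-based economic evaluation methods". The second says that the output will be expected costs (intervention against health care and family costs), "effectiveness, and cost-effectiveness ratio with uncertainty around such values in terms of credible intervals". Credible intervals are therefore planned for three quantities: cost, effectiveness and their ratio.

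The section does not say which effect measure is the denominator, and it has no rule for draws that fall in more than one quadrant of the cost-effectiveness plane. Statistical software and versions lists packages likely to be used, ending with "mice, Amelia, boot, heemod, BCEA", but specifies no output from them.

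**The concern.** The ratio is the cost difference divided by the effect difference. When the distribution of the denominator covers zero, two things go wrong. The ratio is discontinuous at zero, so very large positive and very large negative values lie next to each other in terms of the data. Its sign also loses its meaning: a negative ratio arises both when vitamin D is cheaper and better and when it is dearer and worse. A positive ratio likewise mixes dearer and better with cheaper and worse. Ordering the draws and reading off limits puts opposite conclusions side by side.

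Software will still print two finite limits, so nothing warns the reader. At stake is the uncertainty statement for the headline ratio of a stated secondary objective, in a trial that recruited 37% of its target (323/865).

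**Working it through.** The target of 865 cannot be reproduced, because the SAP gives neither power nor a control-arm mean. I therefore worked backwards from it.

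**Inputs from the SAP**
- Recruitment (Introduction, Design): "Overall, 323 (of the target of 865) children aged 1-5 years".
- Design effect, rate ratio (RR) 0.75 (Analysis objectives): "leads to a 25% relative reduction in the mean number of exacerbations requiring oral corticosteroids (OCS) per child over a 7-month period".
- Effect in the cited 2016 review (Introduction, Background): "rate ratio: 0.63, high-quality evidence".
- Count distribution (Analysis objectives): the number of courses per child "would approximately follow a Poisson distribution". A negative binomial model is planned if there is overdispersion (Primary Efficacy Analyses).
- 1:1 allocation and a two-sided 5% level.

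**Assumptions of mine**
- The effect measure is courses of oral corticosteroids.
- 865 gave 80% or 90% power at RR 0.75.
- The credible level is 95%.
- The prior is weak, so the credible interval for the effect behaves like a confidence interval.

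**Step 1: implied control mean.** With N children in two equal arms, Var(ln RR) = (2/(N·μ0))(1 + 1/RR). Hence μ0 = 2(1 + 1/RR)(z_α + z_β)² / (N·(ln RR)²). At RR 0.75, 1 + 1/RR = 2.333 and (ln RR)² = 0.0828.
- 80% power: 2 × 2.333 × 7.849 / (865 × 0.0828) ≈ 0.51.
- 90% power: 2 × 2.333 × 10.507 / (865 × 0.0828) ≈ 0.68.

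**Step 2: RR 0.75 at 323 children.** The standardised effect shrinks by √(323/865) = 0.611.
- 80% design: 2.80 × 0.611 = 1.71. Power is Φ(1.71 − 1.96) = 0.40, so the interval covers zero with probability 60%.
- 90% design: 3.24 × 0.611 = 1.98. Power is Φ(1.98 − 1.96) = 0.51, so that probability is 49%.

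**Step 3: RR 0.63 at 323 children.** The standardised effect is |ln 0.63| × √(323·μ0 / (2(1 + 1/0.63))), with |ln 0.63| = 0.462 and denominator 5.175.
- 80% design: 0.462 × √(323 × 0.51 / 5.175) ≈ 2.61. Power is 0.74, so the probability is 26%.
- 90% design: 0.462 × √(323 × 0.68 / 5.175) ≈ 3.01. Power is 0.86, so the probability is 14%.

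**Step 4: no effect.** A 95% interval covers zero 95% of the time by construction.

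**Step 5: sensitivity.** For control means from 0.3 to 1.0 and negative binomial dispersion from 0 to 1, the probability runs from 33% to 79% at RR 0.75 and from 4% to 56% at RR 0.63.

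**Step 6: what the output would look like.** This is illustration only, because the SAP has no economic figures. I took a standard error of the effect difference of √((0.5 + 0.375)/161.5) = 0.074, an observed 0.05 courses averted per child, and an independent cost difference with mean 50 and SD 100 currency units. From 1,000,000 draws:

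| Quadrant | Share of draws | Sign of ratio |
|---|---|---|
| Dearer, better | 52.0% | + |
| Cheaper, better | 23.1% | − |
| Cheaper, worse | 7.7% | + |
| Dearer, worse | 17.2% | − |

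The 95% percentile interval of the ratio is about −15,100 to 15,800. Negative ratios make up 23.1 + 17.2 = 40.3% of draws. Of these, 57% are cheaper and better, and 43% are dearer and worse.

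On the same draws, incremental net benefit (λ × effect difference − cost difference) can be read directly:
- λ = 1,000 per course averted: mean 0 (95% −243 to 244), probability cost-effective 0.50.
- λ = 5,000: mean 200 (−547 to 949), probability 0.70.

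**The case against.** A reader might go further and infer that the ratio is the whole economic result, and that a meaningless interval is the likely outcome at 323 children. The SAP supports neither inference.

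- **Scope.** Cost and effectiveness get credible intervals of their own, and these can be read whatever the ratio does.
- **Likelihood.** The SAP gives no power, control mean or effect measure. Under the usual power assumptions the chance is about even at the design effect, and it is well below one half at 0.63, the only effect estimate that the SAP quotes. The 95% figure applies only if vitamin D has no effect.
- **What the percentages measure.** They are the chance that the effect interval covers zero. They are not the chance that the printed interval is infinite: limits taken from draws are always finite, and the SAP does not say how the limits will be formed.
- **Detail elsewhere.** A willingness-to-pay range, a plane or an acceptability curve could sit in the protocol or an economic plan, neither of which is at hand. Their absence here is not a fault in itself. The generic methods sentence and the listing of BCEA leave room for them.

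All of this stands and limits the point. It does not remove it. The SAP itself names the ratio and commits to a credible interval around it, and a package that is only likely to be used does not replace that commitment.

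**Conclusion.** The point holds for one of the three planned economic summaries. An interval on the ratio can be read only if the effect difference is clearly away from zero, and the SAP makes no provision for the other case. With 323 of 865 children that case is a real prospect: about 49-60% if the true rate ratio is 0.75, 14-26% if it is 0.63, and 95% under no effect.

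These figures assume corticosteroid courses as the effect measure, 80-90% design power, Poisson counts and a weak prior. Varying the control mean and dispersion widens them to 33-79% at 0.75 and 4-56% at 0.63. The documents do not show that it is the likely case. The primary, efficacy and safety analyses are unaffected. The change is worth making because the failure can be foreseen, would not show in the printed output, and is cheap to avoid.

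**What to change.** Amend the second sentence under Ancillary studies so that the economic evaluation reports:
- the effect measure used as denominator, by name;
- incremental cost and incremental effect, each with a credible interval, and their joint draws on the cost-effectiveness plane;
- incremental net monetary benefit with credible intervals over a stated willingness-to-pay range, and an acceptability curve;
- the ratio as a point estimate only, with no interval when draws span quadrants.

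This takes a sentence or two and no new data, since the outputs come from the same draws. The one added burden is that a willingness-to-pay range must be chosen and written down. If the protocol or a separate economic plan already specifies these outputs, the SAP should refer to it and drop the interval on the ratio.

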Appendix 1: Primary outcome variable coding

Primary outcome (OCS)

Suggested wording for use in manuscripts:

The primary outcome was number of short courses of systemic corticosteroids (OCS) prescribed for asthma during the 7-month intervention period, as confirmed by hospital and/or pharmacy records (or exceptionally, reported by parents and determined to be credible by an independent clinician).

Sources of OCS events

OCS could be documented in a number of places in the study CRFs including:

REDCap database:

- Med Examination CRF (to be considered administered or prescribed prior to randomization);
- Visit and Phone Contact CRF;
- CRF OCS in Medical Records (Clinic visit 1) – should contain info about OCS dated PRIOR to Randomization, to be verified in case any typos/mistakes have been done during the data entry;
- CRF OCS in Medical Records at end of study;
- CRF Pharmacy Report (Clinic visit 1) – should contain info about OCS dated PRIOR to Randomization, to be verified in case any typos/mistakes have been done during the data entry;
- CRF Pharmacy Report at end of study;
- CRF Additional cold or asthma flareup (main redcap).

REDCap3 database (parent-reported):

- CRF Cold and Asthma Flare Up Diary For Young Children;
- CRF Summary of an asthma flare-up or cold.

Validation of OCS events

Timing:

To be considered an outcome, an OCS must be administered or prescribed after randomization but could include the day of randomization, provided it was not prescribed on the MEDEX par the study physician and there was credible information of its administration/prescription after the time of rerandomization, until (and including) the last day of the follow up window. For the purposes of OCS use, the end of the follow up window is either the date of visit 3, or if the visit 3 did not occur, the randomization date plus 7 months.

Completeness of the data:

The complete information about OCS includes the name of the medication, dose, daily frequency, duration, and route as well as reason.

Relationship with an asthma exacerbation:

(1) Inclusion

- OCS use requires a medical documentation (MedRec CRF) or by the parental report (verbally recorded in VPC or on ADYC) that the reason for its use is asthma related, defined as:
 - i. Asthma flare-up, Asthma-like diagnoses (bronchospasm, airway hyperactivity, bronchiolitis, bronchitis, wheezing, pneumonia, etc.);
 - ii. Other diagnosis (Pneumonia, Otitis) as such indication would suggest a co-existing diagnosis of asthma
 - iii. Unknown: Handling of unconfirmed reasons of OCS use. Unless otherwise confirmed, all OCS uses will be assumed to be for asthma (i.e., pharmacy dispensing of OCS without parental report or medical record of reason for use), given the high prior probability of this reason in included participants.

(2) Excluded:

- OCS administered for treatment of conditions or other respiratory conditions (e.g. cutaneous conditions, adrenal insufficiency, anaphylaxis (anaphylactic shock), kidney disease, serum sickness, surgery, croup' or 'laryngitis' etc.) as documented in eCRF OCS documented in the medical Record (1st priority), Visit and phone contacts (less priority as self-reported) or ADYC will be excluded. Of note, if prescribed in Med examination (eCRF), then it is clearly for asthma.

Handling of Special cases

Denied administration of prescribed or dispensed OCS by parents:

If parents deny administration of identified OCS prescribed or dispensed by pharmacy, the OCS will be counted as an OCS use for the primary outcome, as per the physician intention for the child to use OCS, as this intention is the marker of moderate or severe exacerbation. (qu 10 et 11)

Delayed administration of prescribed or dispensed OCS by parents

If parents credibly report of an alternate start date than that documented in pharmacy records (for example, medication dispensed ahead of time for subsequent use as part of an action plan or prior to travel), the actual date of OCS use will be reported by parents in VPC CRF (or ADYC), and this date will be considered for primary outcome calculation. Such credible report should be documented in VPC CRF by the nurse. In this case, the concordance between the information provided verbally (VPC) or in writing (ADYC) by parents regarding the reason for, and information about, the OCS prescription will be cross-verified with the documentation of the original prescription in med records CRF (reason, name and dosage)—preferred approach—and/or Pharmacy report (OCS name, dose, duration)—secondary approach as the Pharmacy report that does not provide the reason for its prescription. If

the date of initiation has not occurred before or at Visit 3, the OCS would not be considered as OCS use during the study period. (qu 10.2.6.2)

If **pharmacy records were never obtained**, we will consider accepting the OCS medications as described in the Clinic and Phone contacts eCRF, provided that the information is considered credible by the nurse and the reported reason is concordant with other document (med records or parental report) about the OCS.

Of note, given the potential subjectivity of the judgement of 'credibility', these approaches will be independently coded by two biostatisticians, to identify any rule resulting in discrepancy. Any rule resulting in discrepancies will be identified; and all OCS events in which these rules applied would be independently assessed by an independent adjudicator, whose decision will be final.

[Events with multiple 'courses'](#)

Each record of a possible OCS course will be extracted from the CRFs and added to a long file with a source, reason for administration, type of documentation, start and end date.

Once all CRF sources have been extracted, OCS courses will be evaluated to determine if they represent one event or multiple events.

Any occurrence of two or more 'courses' (whether administration, prescription, dispensing, or parent-administered), initiated with a 7-day period (between the beginning of 1st course and the beginning of the 2nd course) or within a 2-day period (between the end of a 1st course and the beginning of the 2nd course) which ever if longest, will be counted only once (and assumed to be for the same exacerbation). These approaches will be independently coded by two biostatisticians, to identify any rule resulting in discrepancy. Any rule resulting in discrepancies will be identified; and all OCS events in which these rules applied would be independently assessed by an independent adjudicator, whose decision will be final.

Following the double-coding approach, the team of [name] will prepare the list of documented OCS, in a wide format, showing all sources of OCS reporting:

- Medical Examination,
- OCS in Medical records,
- Pharmacy Report
- Visit and Phone Contact,
- Additional cold and asthma flare-up (ACAFU)
- Asthma Flare-up Diary for Young Children (ADYC) (REDCap3)
- Summary of an asthma flare-up or cold (SAF) (REDCap3)

The information from REDCap3 (ADYC and Summary CRF) will be merged with the main list of the OCS to detect special cases when information is credibly reported in REDCap3, but missing in REDCap main database.

The list of variables related to the primary outcome calculation, including conditions to verify, is available in the [Appendix](#).

CRF specific coding rules:

- Visit and Phone Contact
phcon_steroid, phcon_steroid_2, phcon_steroid2 and phcon_steroid2_2 = 1 were used to select records where an OCS was indicated
Exclude records where reason for systemic steroids was = 2 (other condition)
ocs_start=phcon_steroid_startdat,
ocs_end=phcon_steroid_enddat,
- Med Examination
- OCS in Medical Records
ocsdoc_v1_syst_yn used to select records where an OCS was indicated
- OCS in Medical Records end of study
ocsdoc_end_syst_y used to select records where an OCS was indicated
Exclude records where reason for systemic steroids was not 1, 2 or 4, (3 was Laryngitis)
[ocsdoc_end_reason] assuming for this source that
 - if OCS is only administered, then the start date is the administration date and the duration should consider the total number of days administered as reported in qu1.1.6 (# days administered or given) including the start date
 - if only prescribed, start date is prescription date and end date calculated with the duration of prescription including prescription date.
 - if both administered and prescribed, then start date is the administration date, the total number of days considered administered is 1.1.6 (# days administered or given) and the start day of prescription is included in the duration of the prescribed medication.
 - if only prescribed, then total number of days considered date prescribed + #days prescribed - 1
- if both administered and prescribed, provide information (name, duration, etc) for each OCS
- Pharmacy Report
- Pharmacy Report end of study reporting OCS name, dose, date and number of days of prescription
- Additional cold or asthma flareup (REDCap)
- Asthma Flare-up Diary for Young Children (ADYC) (REDCap3)
- Summary of an asthma flare-up or cold (SAF) (REDCap3)

Specific variables used by CRF source

Visit and Phone Contact CRF

Variable / Field Name /	Field Attributes (Field Type, Required)
-------------------------	---

Field Label	Validation, Choices)	
10. Is the child currently taking, or have he/she taken oral, intravenous, or intramuscular STEROIDS since the last contact? [phcon_steroid_2]	1: Yes 0: No	Should be yes
10.1 What was the reason for SYSTEMIC STEROIDS due to: [phcon_steroid_reas]	1: a. Asthma flare-up 4: b. Asthma-like diagnoses (broncho-spasm, airway hyperreactivity, bronchio-litis, or wheezing) 2: c. Other condition: (record in AHE) 3: d. Unknown	Should not be a missing value
10.1.1 Other condition: [phcon_steroid_4]	text	Should include "bronchospasm, airway hyperactivity, bronchiolitis, bronchitis, wheezing, pneumonia , otitis".
10.2 Medication (Use the generic name(s), NOT trade name(s): (To be documented when interviewing parents, but the generic name MUST be entered before submitting the form): [phcon_steroid_mednam]	1: Prednisone tablet 2: Prednisolone (Pediapred®) 3: Dexamethasone (solution or tablet) 4: Methylprednisolone (solution or tablet) 5: Solucortef 6: Other	Should not be a missing value
10.2a If other, specify: [phcon_steroid_mednam_2]	text	Should not include cefodox / magnesium sulfate / hydrocortisone, other cutaneous, nasal, ophthalmic (etc.) preparation.
10.2.1 Route: [phcon_steroid_medrout]	1: Oral 2: IV 3: IM	Should not be a missing value

10.2.2 mg per dose - - - . _ mg [phcon_steroid_meddos]	text (number)	Should not be a missing value
10.2.3 Frequency (#times/day): [phcon_steroid_medfreq]	1:1 2:2 3:3 4:4	Should not be a missing value
10.2.4 Start date: [phcon_steroid_startdat]	text (date_ymd)	Should not be a missing value
10.2.5 End date: [phcon_steroid_endat]	text (date_ymd)	Should not be a missing value
10.2.6 According to parents, the medication was administered or served by (Both answers are possible) Selon les parents, le médicament a-t-il été administré ou servi par (les deux réponses sont possibles)	[phcon_steroid_servby__1]1: Pharmacy [phcon_steroid_servby__2]1: Hospital	Should not be a missing value
10.2.6.1 Confirmation of dispensing obtained by pharmacy records: If awaiting until the end of study to obtain pharmacy records, leave this question unanswered until then [phcon_sterconfby_pharm]	1: Yes 2: No 3: Pharmacy records never obtained	Should not be a missing value
10.2.6.2 Date of dispensing based on [phcon_sterconfby_pharm_date]	1: Pharmacy records 2: Credible report by parents of an alternate start date than that documented in pharmacy records (for example, medication dispensed ahead of time for subsequent use as part of an action plan) 3: Credible report by parents of denied administration of prescribed or dispensed 4: Unconfirmed as pharmacy	Should not be a missing value

	records NEVER obtained	
10.2.6.3 Confirmation of administration with/without dispensing obtained from hospital: If awaiting until the end of study to obtain hospital/clinic records, leave this question unanswered until then [phcon_sterconfby_hrec]	1: Yes 2: No 3: Hospital/clinic Records NEVER obtained	Should not be a missing value
10.2.6.4 Date of administration/dispensing confirmation based on [phcon_sterconfby_hosp_date]	1: Hospital/clinic records 2: Credible report by parents of an alternate start date (for example, medication dispensed ahead of time for subsequent use as part of an action plan) 3: Credible report by parents of denied administration of prescribed or dispensed medication 4: Unconfirmed as hospital / clinic records NEVER obtained	Should not be a missing value

Comment: the same coding should be applied to Q11- Q11.2.6.4.

Comment 2: in case of missing values, consider imputation if feasible (for example, the missing value for Route can be imputed based on the name of the medication).

Medical Examination CRF

Variable / Field Name / Field Label	Field Attributes (Field Type, Validation, Choices)	Required
9. Are you prescribing or recommending any systemic (oral, iv, im) corticosteroids today for the management of a CURRENT exacerbation? If Yes, specify name of the drug, dose, frequency and duration of treatment.	1: Yes 0: No	Should be Yes

[medex_rec_sys_cort]		
9. a) Systemic Corticosteroids (SCS) [medex_rec_cort_list]	1: Prednisone tablet 2: Prednisolone (Pediapred®) 3: Dexamethasone (solution or tablet) 4: Methylprednisolone (solution or tablet) 5: Other oral corticosteroids (solution or tablet)	Should not be a missing value
9.1 Name of medication [medex_rec_sys_cort_oth]	text	Should not include hydrocortisone or other unrelated medications
9. b) mg per dose, mg [medex_rec_cort_strength]	text, Required	Should not be a missing value
9. c) Frequency (#times/day) [medex_rec_cort_freq] #times/day	text	Should not be a missing value
9. d) Duration of treatment [medex_rec_cort_dur]	1: 1 day 2: 2 days 3: 3 days 4: 4 days 5: 5 days 6: >5 days	Should not be a missing value

Additional Cold or Asthma Flare-up CRF

Variable / Field Name / Field Label	Field Attributes (Field Type, Validation, Choices)	Required
8.1.1 What was the reason for SYSTEMIC STEROIDS due to: [acafu_steroid_reas]	1a. Asthma flare-up, specify episode # below 2b. Asthma-like diagnoses (bronchospasm, airway hyperreactivity, bronchiolitis, bronchitis, wheezing, or pneumonia) 3c. Other condition: (record in AHE) 4d. Unknown	Should not be a missing value

8.1.1.1 Other condition: [acafu_steroid_oth]	text	Should include “bronchospasm, airway hyperactivity, bronchiolitis, bronchitis, wheezing, pneumonia , otitis”.
8.1.2 Medication (Use the generic name(s), NOT trade name(s): (To be documented when interviewing parents, but the generic name MUST be entered before submitting the form): [acafu_steroid_mednam]	1Prednisone tablet 2Prednisolone (Pediapred®) 3Dexamethasone (solution or tablet) 4Methylprednisolone (solution or tablet) 5Solucortef 6Other	Should not be a missing value
8.1.2.1 If other, specify: [acafu_steroid_mednam_oth]	text	Should not be a missing value
8.1.3 Route: [acafu_steroid_medrout]	1Oral 2IV 3IM	Should not be a missing value
8.1.4 mg per dose: [acafu_steroid_meddos] _____.____mg	text (number)	Should not be a missing value
8.1.5 Frequency (#times/day): [acafu_steroid_medfreq]	11 22 33 44	Should not be a missing value
8.1.6 Start date: [acafu_steroid_startdat]	text (date_ymd)	Should not be a missing value
8.1.7 End date: [acafu_steroid_endat]	text (date_ymd)	Should not be a missing value
8.1.8 According to parents, the medication was administered or served by (Both answers are possible)	acafu_steroid_servby____1: Pharmacy: 1 acafu_steroid_servby____2: Hospital: 1	Should not be a missing value
8.1.8.1 Confirmation of dispensing obtained by pharmacy records: [acafu_sterconfby_pharm]	1Yes 2No 3Pharmacy records never obtained	Should not be a missing value

8.1.8.2 Date of dispensing based on: [acafu_stecnfby_pharm_date]
	
1Pharmacy records 2Credible report by parents of an alternate start date than that documented in pharmacy records (for example, medication dispensed ahead of time for subsequent use as part of an action plan) 3Credible report by parents of denied administration of prescribed or dispensed 4Unconfirmed as pharmacy records NEVER obtained
	
Should not be a missing value


8.1.8.3 Confirmation of administration with/without dispensing obtained from hospital: [acafu_stercnfby_hosp] If awaiting until the end of study to obtain hospital/clinic records, leave this question unanswered until then
	
1Yes 2No 3Hospital/clinic Records NEVER obtained
	
Should not be a missing value

8.1.8.4 Date of administration/dispensing confirmation based on: [acafu_stecnfby_hosp_date]
	
1Hospital/clinic records 2Credible report by parents of an alternate start date (for example, medication dispensed ahead of time for subsequent use as part of an action plan) 3Credible report by parents of denied administration of prescribed or dispensed medication 4Unconfirmed as hospital/clinic records NEVER obtained
	
Should not be a missing value

Comment: the same coding should be applied to Q8.2 – Q8.5.

Variable / Field Name / Field Label	Field Attributes (Field Type, Validation, Choices)	Required
1. Has there been any administration and/or prescription of systemic (oral, IM, IV) corticosteroids (OCS*) documented in the medical record for asthma or asthma-like symptoms since randomization until V3 (or 7 months after randomization if premature discontinuation) ? [ocsdःdoc_end_syst_yn]	1Yes 0No	Should be Yes
Was the OCS: (choose all that apply)	ocsdःdoc_end_syst_y_1 1:administrated (or given to patient) ocsdःdoc_end_syst_y_2 1: prescribed (to be filled by community pharmacy)	Should not be a missing value
1.1.1 Date of administration (1st dose) [ocsdःdoc_end_adm_date]	text (date_ymd), Required	Should not be a missing value
1.1.2 Medication (use the generic or trade name) [ocsdःdoc_end_med]	1Prednisone tablet 2Prednisolone (pediapred) 3Dexamethasone (solution or tablet) 4Methylprednisolone (solution or tablet) 5Other	Should not be a missing value
1.1.2 a) If other, specify[ocsdःdoc_end_med_oth]	text	Should not include hydrocortisone or other unrelated medications
1.1.3 Route[ocsdःdoc_end_route]	1Oral 2IV 3IM	Should not be a missing value
1.1.4 mg per dose[ocsdःdoc_end_mg] mg	text, Required	Should not be a missing value
1.1.5 What was the reason for	1a) Asthma flare-up	Should not include

SYSTEMIC STEROIDS due to: [ocsdoc_end_reason]	2b) Asthma-like symptoms: bronchospasm, airway hyperactivity, bronchiolitis, bronchitis, wheezing, pneumonia 3c) Laryngitis 4d) Unknown	Laryngitis
1.1.6 Total number of doses administered or given to parents by health care provider (for example include a dose of dexamethasone to give at home by parents) [ocsdoc_end_nb_dos] # doses	text	Should not be a missing value
1.1.7 Was the dose accompanied by a prescription (to be filled by community pharmacy), as documented in the medical chart? [ocsdoc_end_pres]	1Yes 0No	Should not be a missing value
1.1.7.1 Date of prescription[ocsdoc_end_pres_date]	text (date_ymd), Required	Should not be a missing value
1.1.7.2 Medication (Use the generic name(s), NOT trade name(s)): [ocsdoc_end_pres_med]	1Prednisone tablet 2Prednisolone (Pediapred®) 3Dexamethasone (solution or tablet) 4Methylprednisolone (solution or tablet) 5Solu cortef 6Other	Should not be a missing value
1.1.7.2 a) If other, specify[ocsdoc_end_pres_med_oth]	text	Should not include hydrocortisone or other unrelated medications
1.1.7.3 Route[ocsdoc_end_pres_route]	1Oral 2IV 3IM	Should not be a missing value
1.1.7.4 Total daily dose in mg[ocsdoc_end_pres_tot_mg]	text	Should not be a missing value

mg		
1.1.7.5 Prescription duration (# days) [ocsdoc_end_pres_dur] days	text	Should not be a missing value

Comment: the same coding should be applied to information about Medication 2 (Q1.2.1 - Q1.2.7.5) and Medication 3 (Q1.3.1 - Q1.3.7.5).

Pharmacy Report / End of Study CRF

Variable / Field Name / Field Label	Field Attributes (Field Type, Validation, Choices)	Required
Section Header: Oral Corticosteroids (OCS) Medication	1 Yes 0 No	Should be Yes
1. Has there been any serving of oral corticosteroids (OCS) medication since randomization until V3 (or 7 months after randomization if premature discontinuation) ? [pharm_ocs_end]		
1.1.1 Date of dispensing [pharm_ocs_end_dat_disp_1]	text (date_ymd), Required	Should not be a missing value
1.1.2 Medication (use the generic or trade name) [pharm_ocs_end_nam_1]	1 Prednisone tablet 2 Prednisolone (pediapred) 3 Dexamethasone (solution or tablet) 4 Methylprednisolone (solution or tablet) 5 Other (specify DIN)	Should not be a missing value
1.1.2 a) Specify [pharm_ocs_end_nam_1a]	text	Should not include hydrocortisone or other unrelated medications

1.1.4 mg per dose [pharm_ocs_end_dos_1] mg	text, Required	Should not be a missing value
1.1.5 Frequency (#times/day) [pharm_ocs_end_freq_1] #times/day	text	Should not be a missing value
1.1.6 Prescription duration (#days) [pharm_ocs_end_dur_1] days	text	Should not be a missing value
1.1.7 Date of the prescription [pharm_ocs_end_date_1]	text (date_ymd), Required	Should not be a missing value

Comment: the same coding should be applied to information about Medications 2 - 6 (Q1.2.1 - Q1.2.7; up to Q1.6.1 - Q1.6.7).

